| 3 | Staying about the same |
| 4 | Getting somewhat better |
| 5 | Getting much better |
| 6 | Completely gone |

Answering “No” to question 5 obviates questions 6-7. Similarly, answering “Yes” to question 5 causes the responses to questions 6-7 to be summed in the resulting overall score. A failure to answer question 5 would render responses to questions 6-7 problematic. Question 5 is the gatekeeper question and question 6-7 will be referred as subsequent questions.

The full list of gatekeeper questions is:

- Question 1: Gatekeeper to questions, 2, 3, 4
- Question 5: Gatekeeper to question 6, 7
- Question 16: Gatekeeper to questions 17, 18, 19
- Question 20: Gatekeeper to questions, 21, 22, 23
- Question 27: Gatekeeper to question 28
- Question 29: Gatekeeper to question 30

A domain score will be deemed as missing if:

1. Answering “No” or “Never” to gatekeeper question but non-missing responses to any of the subsequent questions.
2. Answering “Yes” to gatekeeper question but 1 or more missing responses to subsequent questions, with the exception of missing responses to question 6 which will be scored as 0.
3. Missing response to gatekeeper question and 1 or more missing responses to subsequent questions.
4. Multiple responses to the same question within a domain, with the exception of question 6 that says, “check all.”
5. Missing response to a question within a domain that is not part of a gatekeeper/ subsequent question set. These questions are: 8, 9, 10, 11, 12, 13, 14, 15, 24, 25, 26, 31. The exception is when both questions 9 & 10 are answered as “No” and question 11 is missing, the score will be 0.

When a gatekeeper question is missing response, but all subsequent questions are non-missing, the gatekeeper question will be imputed as “Yes” or the max impairment (example: “Constantly” for questions 27 and 29). For questions 9, 10, and 11, if both questions 9 and 10 are missing responses and the response to question 11 is “1,” question 9 & 10 will be imputed as “No.” For all other responses, question 9 & 10 will be imputed as “Yes.”

For each patient, if ≤ 2 domain scores are missing, the total score will be calculated by imputing the missing domain score by the average domain score using data from any of the patients who

had non-missing score for that domain at the time point. If more than 2 domain scores are missing, the total score will be deemed as missing.

The full text of the COMPASS-31 is below.

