15. In the past year, have you had a cramping or colicky abdominal pain?

- 1 Never
- 2 Sometimes
- 3 A lot of the time

16. In the past year, have you had any bouts of diarrhea?

- 1 Yes
- 2 No (if you marked No, please skip to question 20)

17. How frequently does this occur?

- 1 Rarely
- 2 Occasionally
- 3 Frequently _____ times per month
- 4 Constantly

18. How severe are these bouts of diarrhea?

- 1 Mild
- 2 Moderate
- 3 Severe

19. Are your bouts of diarrhea getting:

- 1 Much worse
- 2 Somewhat worse
- 3 Staying the same
- 4 Somewhat better
- 5 Much better
- 6 Completely gone

20. In the past year, have you been constipated?

- 1 Yes
- 2 No (if you marked No, please skip to question 24)

21. How frequently are you constipated?

- 1 Rarely
- 2 Occasionally
- 3 Frequently _____ times per month
- 4 Constantly

22. How severe are these episodes of constipation?

- 1 Mild
- 2 Moderate
- 3 Severe

23. Is your constipation getting:

- 1 Much worse
- 2 Somewhat worse
- 3 Staying the same
- 4 Somewhat better
- 5 Much better
- 6 Completely gone

24. In the past year, have you ever lost control of your bladder function?

- 1 Never
- 2 Occasionally
- 3 Frequently _____ times per month
- 4 Constantly

25. In the past year, have you had difficulty passing urine?

- 1 Never
- 2 Occasionally
- 3 Frequently _____ times per month
- 4 Constantly

26. In the past year, have you had trouble completely emptying your bladder?

- 1 Never
- 2 Occasionally
- 3 Frequently _____ times per month
- 4 Constantly

27. In the past year, without sunglasses or tinted glasses, has bright light bothered your eyes?

- 1 Never (if you marked Never, please skip to question 29)
- 2 Occasionally
- 3 Frequently
- 4 Constantly

28. How severe is this sensitivity to bright light?

- 1 Mild
- 2 Moderate
- 3 Severe

29. In the past year, have you had trouble focusing your eyes?

- 1 Never (if you marked Never, please skip to question 31)
- 2 Occasionally
- 3 Frequently
- 4 Constantly

30. How severe is this focusing problem?

- 1 Mild
- 2 Moderate
- 3 Severe

31. Is the most troublesome symptom with your eyes (ie, sensitivity to bright light or trouble focusing) getting:

- 1 I have not had any of these symptoms
- 2 Much worse
- 3 Somewhat worse
- 4 Staying about the same
- 5 Somewhat better
- 6 Much better
- 7 Completely gone

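### The COMPASS-31 rules score a blank Q11 as 0 in a symptom-free patient but give Q31 no such exception, so that patient takes other patients' mean instead of 0

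*SAP*

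**What the plan says.** SAP 7.1.4 lists five conditions that make a COMPASS-31 domain score missing. The fifth covers blanks in items outside the gatekeeper sets, and its list includes questions 11 and 31. It carries one relief: "The exception is when both questions 9 & 10 are answered as “No” and question 11 is missing, the score will be 0". When no more than two domains are missing, each is replaced by the average of the patients who have that domain score at the same time point. With more than two missing, the total is missing.

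Questions 27 (bright light) and 29 (focusing) open the pupillomotor domain and are listed as gatekeepers: "Question 27: Gatekeeper to question 28" and "Question 29: Gatekeeper to question 30". Their answers are Never, Occasionally, Frequently and Constantly. Question 27's first option reads "Never (if you marked Never, please skip to question 29"); Never on question 29 sends the patient to question 31. Question 31 asks how the worse of the two symptoms is changing, and its first option is "I have not had any of these symptoms", which the scoring text sets at 0.

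The second condition is triggered by "Answering “Yes” to gatekeeper question but 1 or more missing responses to subsequent questions".

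Under SAP 3.10.1 the results of these partial imputations feed all analyses. SAP 4.4.2.3 analyses change from baseline in the total by MMRM.

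**The concern.** Questions 11 and 31 do the same job. Each follows two symptom questions, asks for the time course, and offers an option for patients who never had the symptom. The SAP foresaw that a patient with neither symptom might leave question 11 blank, and scored that blank 0. It did not do so for question 31. The patient's own answers fix the pupillomotor score at 0, yet the rule discards them and substitutes a value from other patients, some of whom have symptoms.

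Three things follow:
- The patient's total is too high by the imputed mean.
- If the blank occurs at one visit only, a stable patient shows a false change: worsening if the blank is after baseline, improvement if it is at baseline.
- The record spends one of the two missing domains allowed, so a patient with two other missing domains loses the total.

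A smaller gap lies nearby. The second condition turns on Yes, which questions 27 and 29 do not offer, so the text does not settle what happens when a symptomatic patient leaves the severity item (28 or 30) blank.

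**Working it through.** **Scale check.** Inputs are the weights and item scoring in SAP 7.1.4. The item maxima for questions 8, 12–15 and 24–26 are my reading of the scoring text. Raw maximum × weight by domain:
- Orthostatic: 10 × 4.0 = 40
- Vasomotor: 6 × 0.83333333 = 5
- Secretomotor: 7 × 2.1428571 = 15
- Gastrointestinal: 28 × 0.8928571 = 25
- Bladder: 9 × 1.1111111 = 10
- Pupillomotor: (3+3+3+3+3) × 0.3333333 = 5

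The sum is 100, which reproduces the SAP's stated maximum. The pupillomotor domain therefore runs from 0 to 5.

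**The two items side by side.**

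| | Q11 (dry eyes or mouth) | Q31 (light or focusing) |
|---|---|---|
| Preceding symptom items | Q9, Q10 | Q27, Q29 |
| Answer when symptom-free | No | Never |
| Option for never having had the symptom | yes, scored 0 | yes, scored 0 |
| On the list of items whose blank makes the domain missing | yes | yes |
| Blank scored 0 when symptom-free | yes | no |

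**The symptom-free record.** Take Q27 = Never, Q28 skipped, Q29 = Never, Q30 skipped, Q31 blank.
- The first condition does not fire, because Q28 and Q30 are blank as instructed.
- The second and third do not fire, because neither gatekeeper is positive or missing.
- The fourth does not fire, because there are no multiple responses.
- The fifth fires on Q31, so the domain is missing.

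The consistent score is (0 + 0 + 0) × 0.3333333 = 0. The assigned score is m, the mean of the other patients at that visit, with 0 ≤ m ≤ 5.

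**Effect on the group mean.** With 20 patients (SAP 3.1), one such record, and the other 19 averaging m:
- as written: (19m + m)/20 = m
- with the true 0: 19m/20
- difference: m/20

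The documents give no m. At assumed values of 1, 2, 3 and 5 the difference is 0.05, 0.10, 0.15 and 0.25 points. The last needs every other patient at the domain maximum. With 16 patients the divisor is 16, and the ceiling is 5/16 = 0.31.

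**The severity blank (Q28 or Q30).** Suppose Q27 is answered other than Never and Q28 is blank. There are two ways to score it.
- *Sum the answered items.* Severity is scored 1 to 3, so one blank loses 1 × 0.3333 to 3 × 0.3333 = 0.33 to 1.00 points.
- *Set the domain to missing and impute m.*

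To compare them I listed every internally consistent pupillomotor record (397), kept the 360 with Q27 symptomatic, and blanked Q28. Records are weighted equally, which is an assumption.

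| Method | Mean absolute error (points) |
|---|---|
| Sum the answered items | 0.67 |
| Impute, m = 1 | 2.04 |
| Impute, m = 1.5 | 1.55 |
| Impute, m = 2 | 1.11 |
| Impute, m = 2.5 | 0.77 |

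With both severities blank (324 records), summing has a mean absolute error of 1.33. Imputation gives 2.17, 1.67, 1.18 and 0.78 at the same four values of m. Neither method is uniformly better.

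**The case against.** On question 31, the best defence is that the fifth condition is explicit, any two programmers would apply it alike, and the form leads the patient to an item with a suitable option, so a blank is a genuine omission. All of that is true, and nothing in the documents shows how often such blanks occur. But it applies equally to question 11, where the SAP judged the omission harmless and scored it 0. No reason is given for treating the twin item differently.

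A reader might infer more than the documents support, in three ways:
- *That the rules overlook frequency-type gatekeepers.* They do not. The first condition reads "Answering “No” or “Never” to gatekeeper question but non-missing responses to any of the subsequent questions", and the sentence on a missing gatekeeper gives the "example: “Constantly” for questions 27 and 29". Only the second condition is worded too narrowly.
- *That symptomatic patients with a blank severity are under-scored.* The SAP never says that blank scores 0. Where it wants a zero it says so, for questions 6 and 11, and Yes can be read as any positive answer. The text is open; under-scoring is only one reading of it.
- *That the question 31 gap comes from the frequency format.* It does not. It is a missing exception, and would exist with Yes/No gatekeepers too.

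**Conclusion.** The question 31 point holds on the text. A stated rule replaces a score that the patient's own answers fix at 0 with other patients' mean, and the SAP already treats the parallel item correctly. The effect is small. One record is overstated by m (0 to 5 points), and the group mean by m/20 per affected record, at most 0.25 of 100 points at 20 patients. This assumes that the patient has no more than two missing domains; otherwise the total is lost. It touches one secondary endpoint that SAP 3.2 treats as descriptive, and leaves the primary TTR analysis alone.

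The severity-blank point is a request for clarity, not a demonstrated scoring error. Setting the domain to missing would match the other gatekeepers, but it is not shown to be more accurate than summing the answered items.

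**What to change.** In SAP 7.1.4, extend the exception in the fifth condition with: *and when both questions 27 and 29 are answered Never and question 31 is missing, the score for question 31 will be 0*.

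As a clarification, state in the second condition how a blank question 28 or 30 is handled when question 27 or 29 is answered other than Never. Either choice is defensible if it is fixed before scoring.

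The cost is one added clause, one clarifying sentence and the matching lines of the scoring program. No new data are needed.

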7.2. Pandemic Phase Start Dates by Country

Table 1 Pandemic Phase Start Dates by Country

Country	Date of 1 st Confirmed Case
France	2020-01-24
Germany	2020-01-28
Italy	2020-01-29
Portugal	2020-03-02
Spain	2020-01-31
Sweden	2020-01-31
United Kingdom	2020-01-31

As reported by the World Health Organization and the Taiwan Centers for Disease Control.

8. AMENDMENT HISTORY

Amendment 1: 08 October 2020

Key changes were made to the original SAP to address the impact of the COVID-19 pandemic, including:

- Addition of Per Protocol Analysis Set.
- Updates of using LOCF method for the analyses of NIS, Norfolk QoL-DN, R-ODS and mBMI efficacy endpoints, and using MMRM method for the analysis of COMPASS-31 efficacy endpoint.
- Addition of summaries and analyses to characterize the impact of the COVID-19 pandemic.

Section	Description	Rationale
Section 2.1	Per Protocol Analysis Set was added.	The Per Protocol Analysis Set was added to support primary analyses of estimating treatment effects of secondary and exploratory efficacy endpoints in patients who did not miss or missed less than or equal to 2 doses of patisiran due to COVID-19.
Section 2.2	A data listing of COVID-19 related protocol deviations was added.	The data listing of COVID-19 related protocol deviations was added to align with regulatory guidance recommendations.
Section 3.9	The potential data censoring for secondary and exploratory efficacy endpoints on or after the onset of a serious COVID-19 AE was added.	This was to account for the potential impact of COVID-19 on secondary and exploratory efficacy endpoints in addition to the update of using Per Protocol Analysis Set for primary analyses of secondary and exploratory efficacy endpoints.
Section 3.10	Missing efficacy data summaries were added.	This was to account for potential missingness in efficacy data, including missingness due to COVID-19.
Section 4.1	Patient disposition summaries were updated.	Patient disposition summaries were updated to account for discontinuations associated with COVID-19 pandemic.
Section 3.10.1 Section 4.4.2.1 Section 4.4.2.2 Section 4.4.2.4	The primary analysis for the NIS, Norfolk QOL-DN, R-ODS and mBMI efficacy endpoints was updated to use LOCF to impute missing post-baseline values.	The changes from baseline in NIS, Norfolk QOL-DN and R-ODS assessments between Months 9 and 18 and mBMI assessments between Months 3 and 18 were relatively stable in the patisiran arm of the APOLLO study. Thus, the LOCF method was adopted to account for the potential missingness (including missingness related to COVID-19) in NIS, Norfolk QOL-DN, R-ODS and mBMI efficacy endpoints during this study.

Section	Description	Rationale
Section 4.4.2.3	The primary analysis for the COMPASS-31 efficacy endpoint was changed to MMRM.	The changes from baseline in COMPASS-31 total score showed improvement from Month 9 to Month 18 in the patisiran arm of the APOLLO study. Thus, the MMRM method was adopted to account for potential missingness (including missingness related to COVID-19) in COMPASS-31 total score, which assumes data are Missing at Random (MAR).
Section 4.7	Summaries of COVID-19 pandemic general impact and related impacts on efficacy and safety were added.	The summaries were added to assess the impact of COVID-19 in acknowledgement of regulatory guidance.
Section 7.2	A table for the pandemic phase start dates by country was added.	The table was added to support the related by-pandemic-phase analyses.
Throughout document	General data presentation rules were corrected; Wording of selected analyses were updated; MedDRA version was updated to 23.0 or later; CTCAE version was updated to 5.0 or above; Abbreviation list was updated.	The updates were to streamline and clarify planned analyses needed to support overall objectives and address minor errors.

Signature Page for VV-CLIN-005083 v1.0
ALN-TTR02-008 SAP Amend1

Approval	PPD [Redacted] [Redacted] GMT+0000
----------	---------------------------------------

Approval	PPD [Redacted] [Redacted] 28:10 GMT+0000
----------	---

Signature Page for VV-CLIN-005083 v1.0
ALN-TTR02-008 SAP Amend1
